## 9.6 Analyses

### 9.6.1 General Analysis Considerations

The following sections provide a brief overview of the analysis considerations for REPRIEVE (A5332). Prior to the start of enrollment, a detailed Statistical Analysis Plan fully delineates all planned statistical analyses. **In the event of a DSMB recommendation to stop the trial for efficacy at interim review, full analysis and publication of the primary trial results will be prepared based on the frozen data for the DSMB meeting. Subsequent analyses (including a database prepared for future data-sharing requests) will be performed based on the final trial database including all final study termination visits. In the event of a DSMB recommendation to stop for futility, full analysis and publication of the primary trial results will be performed based on the final trial database including all final study termination visits.**

All major treatment comparisons between the randomized groups will be performed according to the principle of "intention-to-treat;" that is, participants will be analyzed (and endpoints attributed) according to the randomized treatment assigned regardless of subsequent changes to that treatment; as-treated analyses will also be performed. Descriptive summaries of the distribution of continuous baseline variables will be presented in terms of percentiles (eg, median, 25th and 75th percentiles), while discrete variables will be summarized in terms of frequencies and percentages. Statistical comparisons will be performed using two-sided significance tests with a 5% Type I error.

Unless otherwise noted, comparison of time to event outcomes will use methods for competing risks, notably Cox proportional hazards models for estimation of cause-specific hazard ratios and Gray's test for comparison of cumulative incidence curves.

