## STATISTICAL CONSIDERATIONS

### Overview Considerations

Overall sample size assumptions: The projected sample size is 5446 persons, or approximately 80% of the total REPRIEVE study sample.

General analysis plans: As comparison groups to address the objectives listed below (eg, groups classified by sex for Objective 1 and by menopause/hormone status for Objective 2) will not have been assigned by randomization, the distributions of baseline characteristics will be compared between groups to help inform the list of characteristics to be included in covariate

.adjusted models specified below. Baseline covariates anticipated to differ by sex (eg, race, hypertension, smoking, substance use, lipids, BMI) [Hattleberg 2014] will be carefully explored and considered, particularly when they are hypothesized to be prognostic for the outcome. Where treatment effect is included in the analysis plan below (eg, statin effect), this variable will use intent-to-treat formulation.

**General monitoring considerations:** Safety of human participants participating in the objectives described will be monitored by the REPRIEVE DSMB as part of the REPRIEVE trial study monitoring plan.

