***Hypothesis B)*** *High-level immune activation will relate to CVD events in HIV, and this association will be stronger in women versus men.* The primary outcome being tested in this sub-objective is the composite clinical outcome of MACE occurring at any time during follow-up. The secondary outcome being tested is the time from randomization to first MACE occurring any time during follow-up. High-level immune activation with respect to each tested biomarker will be classified by the observed highest quartile of the pre-treatment distributions. Fisher's exact test will be used for testing the main effect of immune activation. Taking the sample size of 5446 from the overall sample size assumptions above, there is an expectation of 4084 in the low immune activation group and 1362 (highest quartile) in the high immune activation group. Assuming ~6% of the study sample will experience a MACE event (from control arm incidence estimate of 15/1000 person-years and statin effect hazard ratio of 0.70; see REPRIEVE protocol [section 9.0](#) for more details), with sample sizes as above and a Bonferroni-adjusted significance level of 0.0167, there will be 90% statistical power to detect 5% MACE rate in the low immune activation group compared with 7.8% MACE rate in the high immune activation group (ie, absolute difference of 2.8% pts in MACE rate between groups). Assessing whether the association of baseline immune activation and MACE will be higher in women versus men requires testing for an interaction effect between sex and immune activation (high vs. low) for

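### Appendix IV, Hypothesis 1B: cutting each immune marker at its top quartile loses about 46% of the information if MACE risk rises steadily with the marker

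*Protocol*

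**What the plan says.** Appendix IV, Objective 1, Hypothesis B sets the cut as "High-level immune activation with respect to each tested biomarker will be classified by the observed highest quartile of the pre-treatment distributions". For the association with MACE, "Fisher's exact test will be used for testing the main effect of immune activation". The outcome for that test is binary: "The primary outcome being tested in this sub-objective is the composite clinical outcome of MACE occurring at any time during follow-up".

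The appendix projects 5446 people and splits them accordingly: "there is an expectation of 4084 in the low immune activation group and 1362 (highest quartile) in the high immune activation group". It uses "a Bonferroni-adjusted significance level of 0.0167" and claims 90% power for MACE proportions of 5% and 7.8%.

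Comparing the association between women and men "requires testing for an interaction effect between sex and immune activation (high vs. low) for" MACE, so the same split enters the interaction. The appendix puts the power for an additive interaction at 80%. Logistic and Cox models are named for the interaction and for covariate adjustment, but nothing there returns the marker to its measured scale.

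Hypotheses A and C of the same objective do analyse marker levels or changes on their measured scale, with log transformation where indicated.

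**The concern.** The assays yield continuous values, and the cut is a percentile of the sample rather than a level with a stated clinical or biological meaning. It treats a person at the 1st percentile and one at the 74th as alike, yet separates the 74th from the 76th. If risk is graded, that discards information in a setting where events are scarce and alpha has already been divided by three. At stake is the ability of Hypothesis 1B to detect a modest marker association, and to say anything about how it differs by sex. The trial's primary analysis is not touched.

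**Working it through.** **Inputs.** From Appendix IV, Hypothesis B: 4084 low and 1362 high (total 5446); MACE 5% and 7.8%; alpha 0.0167 (0.05/3). Tests are taken as two-sided from protocol section 9.6.1 ("Statistical comparisons will be performed using two-sided significance tests with a 5% Type I error"), because the appendix does not restate it; the critical value is 2.394. For the interaction: 4.9% risk in men with low activation, main-effect ORs of 2.1 each, interaction OR 1.33, sex-marker association 1.33, 22% women. The documents give neither the marker's distribution nor the shape of its relation to MACE. The base assumption here is a normal marker with log-odds linear in it; other shapes follow.

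**1. The plan's own figures.**
- Pooled proportion = (4084 × 0.05 + 1362 × 0.078)/5446 = 0.0570.
- Null SE = sqrt(0.0570 × 0.9430 × (1/4084 + 1/1362)) = 0.00725.
- Alternative SE = sqrt(0.05 × 0.95/4084 + 0.078 × 0.922/1362) = 0.00803.
- Power = Φ((0.028 − 2.394 × 0.00725)/0.00803) = 90.7%. Exact enumeration of Fisher's test gives 90.4%. The stated 90% reproduces.
- Additive interaction: the joint OR is 2.1 × 2.1 × 1.33 = 5.8653, so RERI = 5.8653 − 2.1 − 2.1 + 1 = 2.6653. A delta-method Wald test gives 80.2% on the OR scale and 79.8% on the RR scale. The stated 80% reproduces.

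**2. Information kept by the cut.** For a normal marker with linear log-odds and upper share q, the share kept is φ(z)²/(q(1 − q)). With q = 0.25, z = 0.674 and φ = 0.3178, this is 0.3178²/0.1875 = 53.9%, a loss of 46%. A median split would lose 36%. With an effect linear in markers of other shapes, the loss runs from 36% (exponential) to 56% (lognormal, sigma 1).

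**3. Power at the plan's effect.** A logistic model with a standard normal marker, solved to give 5% below the quartile and 7.8% above it, has intercept −2.842 and slope 0.286, an OR of 1.33 per SD. (That this matches the plan's interaction OR is coincidence.) The information on the slope is N[E(wx²) − E(wx)²/E(w)] with w = p(1 − p). It gives z = 4.86 and power Φ(4.86 − 2.394) = 99.3%, against 90.7% with the cut. A simulation of 2000 trials gives 99.3% and 90.2% (Fisher).
- For 90% power, the continuous marker needs about 3113 people and the cut 5311 (41% fewer).
- The smallest OR per SD detectable with 90% power at 5446 is 1.24 continuous and 1.33 with the cut.
- Under this model, risk inside the low group runs from 2.9% (1st percentile) to 6.5% (74th); at the 76th it is 6.7%.

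**4. If risk is a step.** With risk at 5% below the quartile and 7.8% above it, and flat within each group, simulated power is 90% for the cut and 66% for a linear continuous term.

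**5. Sex interaction.** With the plan's interaction inputs and a normal marker within each sex, the multiplicative interaction has z = 1.31 with the cut and 1.77 continuous. The share kept is (1.312/1.769)² = 55%, a loss of 45%. Power on that scale is 14% and 27%. Additive power with a continuous marker was not computed; it depends on the increment chosen.

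**The case against.** The strongest reply is that the hypothesis is itself worded about high-level activation, so a top-quartile contrast puts it into practice, while a per-SD slope asks a somewhat different question. That stands in part. The wording allows the contrast but gives no reason to expect a step at the 75th percentile, and risk at high levels can also be read from a fitted continuous model. The reply does justify keeping the quartile comparison in the plan.

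Marker values are also not lost across the appendix. Hypotheses A and C use them as measured, Hypothesis D brings marker data into a structural equation model, and protocol section 9.6.3 plans Cox models for biomarkers and MACE without stating the functional form. The SAP supplied covers only the mechanistic substudy, so a continuous analysis in the main trial's SAP cannot be ruled out.

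Four stronger readings are tempting, and the documents do not support them:
- **That half the information is lost whatever the truth.** The loss depends on graded risk, which the documents neither state nor exclude.
- **That the ancillary study is underpowered because of the cut.** Both stated powers include it. Replacing the appendix's roughly 6% MACE by 288/7500 = 3.84% (the trial's event target over its enlarged sample) gives 77% with the cut and 95% continuous at the same OR per SD. The drop from 91% to 77% comes from the event rate.
- **That the interaction suffers most.** Its relative loss is 45%, against 46% for the main effect.
- **That an observed quartile inflates type I error.** It is a percentile fixed in advance, taken from pre-treatment values without regard to outcome.

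**Conclusion.** The point holds as a conditional inefficiency. Hypothesis 1B dichotomizes continuous markers for both of its tests, gives no threshold to justify this, and names no continuous alternative. If log-odds of MACE rise steadily with the marker, about 46% of the information goes (36% to 56% by marker shape), and power at the planned effect is 91% where 99% was available. The size rests on the assumed linear relation and, for the central figure, on a normal marker. Under a true step at the quartile the ranking reverses. There is no error in the stated powers. Because the objective is ancillary and the change is cheap, this is worth making but not critical.

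**What to change.** Before marker-MACE data are analysed, amend Hypothesis 1B as follows.

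- **Main effect:** make the test the logistic coefficient per SD of the entry marker, log-transformed if its distribution calls for it. Keep the quartile comparison and a spline as prespecified supportive analyses.
- **Sex interaction:** use the continuous marker but stay on the additive scale that the appendix powers, for example RERI for a prespecified increment such as 1 SD, and restate the power. Do not simply add a sex-by-marker product term to the logistic model. That would move, without saying so, from an additive test powered at 80% to a multiplicative one with about 27%.

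No new samples, visits or data are needed. Both power statements in Hypothesis B must be rewritten. The main-effect test would have less power if the truth is a threshold at the quartile; the spline would help to show such a shape but would not restore that power.

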## 9.0 STATISTICAL CONSIDERATIONS

### 9.1 General Design Issues

REPRIEVE (A5332) is a prospective, randomized, double-blind, placebo-controlled, phase III study of the effect of pitavastatin on major cardiovascular events in **PWH** who do not meet current guidelines for statin therapy. The study was originally designed to enroll 6500 participants **with HIV** on stable ART and not eligible for statins as per the 2013 ACC/AHA guidelines. Enrollment was anticipated to take 30 months with study follow-up continuing for approximately 72 months after the enrollment of the first participant. Based on recommendations of the REPRIEVE (A5332) DSMB following their December 2017 review, the study sample size was increased to approximately 7500 participants with follow-up continuing for approximately 84 months after the enrollment of the first participant. Based on recommendations of the NIH and the REPRIEVE DSMB following their December 2018 review, follow-up was extended to 96 months. **Follow-up will now continue until the study reaches the targeted 288 primary MACE events or is otherwise recommended for closure by the DSMB.**

Further, a cap of approximately 2000 participants total enrollment of individuals with very low cardiovascular risk (estimated 10-year ASCVD risk score <2.5%) was implemented to ensure that the final study population reflects the targeted low-to-moderate-risk population. Subsequent to a new recommendation from the NIH, the total enrollment of individuals with low cardiovascular risk (10-year ASCVD risk score <5.0%) was capped at approximately 4200 participants, to ensure that the final study population reflects the targeted low-to-moderate risk population.

All primary analyses will be performed as intention-to-treat and include all participants as randomized.

A complete firewall will be maintained to ensure that investigators have no access to the data. All data will be kept on secure systems at Frontier Science & Technology Research Foundation (FSTRF). A complete description of the firewall procedures, data organization, and security **is** included in the final statistical analysis plan. The plans and procedures will be consistent with NHLBI and NIAID policy with respect to maintenance of data integrity.

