#### 9.4.2 Design Considerations following December 2017 and 2018 DSMB Reviews

In follow-up to their December 2017 review, the REPRIEVE (A5332) DSMB recommended the following actions: 1) to cease study enrollment of patients with 10-year ASCVD risk score less than 2.5%; 2) increase study sample size by approximately 1,000 participants of higher risk population; and 3) increase the follow-up by 1 year now and consider re-evaluation of an additional follow-up extension in the future [implemented following the December 2018 DSMB Review]. These recommendations respond to the higher than anticipated enrollment of participants with very low risk and ensure that REPRIEVE (A5332) will maintain power to detect the targeted effect of interest under a broader range of scenarios for the rate of MACE in the absence of a pitavastatin (control rate). **Specifically, a total of 288 primary MACE endpoints are needed to ensure that the study will have 85% power to detect a hazard ratio of 0.7.**

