the outcome of MACE. To assess power for interaction effect, methods described in [VanderWeele 2012] will be used under the following assumptions: 4.9% of men with low immune activation will have a qualifying MACE outcome; the main effect odds ratios (OR) for sex and immune activation are each 2.1 (eg, 4.9% MACE in one group compared with 9.8% in the other); a multiplicative interaction OR of 1.33; association between sex and high/low immune activation of 1.33; and 22% female enrollment. Based on these assumptions and using a significance level adjusted to 0.0167, the statistical power for additive interaction effect (eg, as excess in relative risk attributed to interaction) is estimated as 80%. Testing for interaction effects and covariate adjusted models will use multivariable logistic regression (for the primary outcome) and Cox proportional hazards regression (for the secondary, time- to-event formulation outcome).

*Hypothesis C)* *Statins will decrease levels of immune activation markers to a greater extent in HIV-infected women versus men.* The outcomes being tested in this sub-objective are the changes from pre-treatment to 1 year of follow-up of the immune activation markers tested. For this hypothesis, statistical interactions of sex and treatment effects will be tested using linear (log transformed as indicated) models, which can also incorporate covariate adjustment. With estimates of 5% per year loss to follow-up, the effective sample size for this sub-aim is 5174 persons. For the biomarker sCD14, standard deviation of the outcome measure for this sub-aim is estimated assuming standard deviation of 1-year measurements same as baseline and intra-person correlation of 0.65. Further, assuming under additivity a 125 ng/mL effect of sex on sCD14 differences at 1 year and the same effect of statins on sCD14 differences at 1 year, there will be 80% power to detect an additive interaction effect of 220 ng/mL.

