*Hypothesis B)* *Among both pre- and post-menopausal HIV-infected women, reduced ovarian reserve (undetectable AMH) will relate to risk of first CVD event.* As in Objective 1B: The primary outcome being tested in this sub-objective is the same composite clinical outcome of MACE occurring any time during follow-up. The secondary outcome being tested is the time from randomization to first MACE. Assuming 22% female enrollment in REPRIEVE and that a negligible proportion of the pre-menopausal women have reduced ovarian reserve such that the ratio of women with adequate versus reduced ovarian reserve is 1:1, then sample sizes for each group will be 599. As per Objective 1B, it is assumed that the overall rate of MACE among women will be 7%. Applying this event rate with the sample sizes above and using Fisher's exact test for analysis, there will be 90% power (at 5% significance) to show a difference of 5% points between groups (namely, 4.5% MACE in one group and 9.4% MACE in the other.) Alternatively, if a significant proportion of the pre-menopausal women have reduced ovarian reserve such that the ratio of women with adequate versus reduced ovarian reserve is 1:4, then sample sizes will be 299 for the adequate ovarian reserve group and 898 for the reduced ovarian reserve group. In this scenario, there will be 90% power to show a difference of 5.7% between groups. Covariate adjusted models for this hypothesis will use multivariable logistic regression for the primary outcome formulation, and Cox proportional hazards modeling for the time-to-initial event formulation.

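### Appendix IV Objectives 1B and 2B still state power from pre-amendment event rates that disagree with each other and exceed the roughly 3.8% MACE implied by the 288-event target

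*Protocol*

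**What the plan says.** **The trial.** Protocol section 9.1 states that "the study sample size was increased to approximately 7500 participants" and that "Follow-up will now continue until the study reaches the targeted 288 primary MACE events or is otherwise recommended for closure by the DSMB". Section 9.4.2 gives the reason: "a total of 288 primary MACE endpoints are needed to ensure that the study will have 85% power" for a hazard ratio of 0.7.

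**Appendix IV, Overview Considerations.** "The projected sample size is 5446 persons, or approximately 80% of the total REPRIEVE study sample".

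**Objective 1, Hypothesis B.** "Assuming ~6% of the study sample will experience a MACE event", derived from 15/1000 person-years in controls and a hazard ratio of 0.70, with a pointer to section 9.0. For 4084 participants with low and 1362 with high immune activation, at alpha 0.0167, it states 90% power for 5% against 7.8%. For the interaction with sex it assumes that "4.9% of men with low immune activation will have a qualifying MACE outcome", odds ratios of 2.1 for sex and for activation, an interaction odds ratio of 1.33, a sex-activation association of 1.33 and 22% women. It states 80% power.

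**Objective 2, Hypothesis B.** With 599 women per group, "it is assumed that the overall rate of MACE among women will be 7" per cent, attributed to Objective 1B. It states 90% power at alpha 0.05 for 4.5% against 9.4%.

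**The concern.** Section 9.0, on which Appendix IV relies, has moved from a fixed-duration design to an event target, with more participants. The appendix's event proportions have not followed. If the trial closes at 288 events, a longer calendar duration does not bring 6% back: 6% of 5446 is 327 events, while 3.84% is 209.

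Three different event levels are also in use within two objectives: about 6% overall, 7% in women, and interaction inputs that imply something higher than either.

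These analyses serve ancillary objective 1.2.3.1. The stated 90%, 80% and 90% are what a reader will use to judge how informative a non-significant result is, above all for the sex interaction.

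**Working it through.** **1. The target.** Schoenfeld events for 85% power at HR 0.70, two-sided 5%: 4(1.960 + 1.036)²/(ln 0.7)² gives 283; Freedman's formula gives 289. At 288 events power is 85.7%. The target is sound, and 288/7500 = 3.84%.

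**2. Source of the 6%.** With rates of 15 and 10.5 per 1000 person-years and the original median follow-up of 4.75 years (section 9.4.1), the mean of 1 − exp(−rate × time) over the arms is 5.9%.

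**3. Reproducing the stated powers.** All tests are two-sided, as in section 9.6.1.
- 1B main effect: simulated Fisher's exact test, 4084 vs 1362, 5% vs 7.8%, alpha 0.0167: **90%**. Weighted overall proportion 5.7%.
- 1B interaction: I take 25% with high activation (top quartile) and 22% women. The association of 1.33 then puts 23.8% of men and 29.3% of women in the high group. The stated odds ratios give the cells below.

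| Cell | Share | MACE |
|---|---|---|
| Men, low | 59.5% | 4.9% |
| Men, high | 18.6% | 9.8% |
| Women, low | 15.6% | 9.8% |
| Women, high | 6.5% | 23.2% |

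  The additive interaction on the odds-ratio scale (RERI) is 2.1 × 2.1 × 1.33 − 2.1 − 2.1 + 1 = 2.665. Its delta-method standard error with N = 5446 is 0.822. Power = Φ(2.665/0.822 − 2.394) = **80%**.
- 2B: Fisher's exact test, 599 per group, 4.5% vs 9.4%, alpha 0.05: **91%**.

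The methods recover the published values, so the changes below come from the inputs.

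**4. Internal disagreement, without using the 288 target.** The table implies 7.7% overall and, among women, (15.55 × 9.76% + 6.45 × 23.2%)/22 = 13.7%. The same hypothesis uses about 6% overall, and 2B uses 7% in women. Scaling the cells to 6% overall (reference risk 3.74%) raises the standard error to 0.899, and power is Φ(2.665/0.899 − 2.394) = **72%**.

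**5. At 3.84% overall, relative effects held.** I use N = 5446 as written, and N = 6000 as 80% of 7500. I assume the ancillary sample has the trial-wide MACE proportion.

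- 1B main effect: ratio 7.8/5 = 1.56. Low-group risk = 0.0384 × 5446/(4084 + 1362 × 1.56) = 3.37%, against 5.25%.
- 1B interaction: reference risk 2.35%; standard error 1.072 (N = 5446) or 1.021 (N = 6000).
- 2B: ratio 9.4/4.5 = 2.09. Women are set either at 3.84% (2.49% vs 5.19%) or, keeping the plan's 7:6 ratio of women to overall, at 4.48% (2.90% vs 6.06%). The group size is 599 or 660 (6000 × 0.22/2).

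| Analysis | Stated | N = 5446 | N = 6000 |
|---|---|---|---|
| 1B main effect | 90% | 73% | 78% |
| 1B interaction | 80% | 54% | 59% |
| 2B, women 3.84% | 90% | 64% | 70% |
| 2B, women 4.48% | 90% | 73% | 76-77% |

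(The last cell varies by a point between simulation runs.)

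**6. The rows do not form one scenario.** The rescaled interaction cells, with a sex odds ratio of 2.1, imply about 7.0% MACE in women. At 7.0%, 2B power with 599 per group is about 91%.

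**7. Absolute gaps held instead, at 3.84%.** 1B: 3.14% vs 5.94%, a ratio of about 1.9, power about 97%. 2B: 1.39% vs 6.29% (the stated 4.9-point gap), a ratio of about 4.5, power over 99%.

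**The case against.** - **288 is a target.** Section 9.1 lets the DSMB recommend otherwise, section 6.2.3 allows it to set a later date, and section 9.6.1 includes events up to the final termination visits in the final database. A reader might infer that the MACE proportion is now fixed at 3.8%; the documents do not say that. At 5% (375 events in 7500), power with the appendix's group sizes and relative effects held would be about 85% for 1B and 77% for 2B with women also at 5%, still below the stated figures.
- **Which effect is held is a choice.** Appendix IV words its 1B and 2B differences in percentage points, and holding those points keeps power high. This stands as arithmetic. It requires much larger ratios than those now implied, and the interaction inputs are themselves odds ratios.
- **No updated rate for women is given.** This stands, and it is why 2B has a wide range.
- **Not all the loss comes from the event target.** For the interaction, about 8 of the 26 points (80% to 72%) come from the older mismatch between 7.7% and 6%.
- **Interpretation is partly protected.** Section 9.6.1 already plans wide use of confidence intervals and conservative reading of supporting analyses. A reader might infer that a null interaction would be reported as no difference between the sexes; nothing in the protocol says so.

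**Conclusion.** The mismatch is certain: Appendix IV's event inputs predate the 288-event target, and they also contradict one another. The stated 90%, 80% and 90% are not supported by the current design.

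The size of the shortfall is conditional. It rests on closure at about 288 events in 7500, the trial-wide MACE proportion applying to the ancillary sample, relative effects being held, and N between 5446 and 6000. On those terms the 1B main effect has about 73-78% power and the interaction about 54-59%. 2B has about 64-77% if 3.8-4.5% of women have MACE, and stays near 90% only at about 7%.

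It would be tempting to conclude that the true powers are 73%, 54% and 64%. The documents do not support that as a joint result: the 54% implies about 7% MACE in women, while the 64% puts women at 3.84%.

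The points affected are ancillary, non-randomised comparisons. The primary analysis and the 288-event calculation are not touched.

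**What to change.** Recompute the power, or the detectable effects, for Objectives 1B and 2B from one coherent set of inputs, each stated:

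1. the ancillary sample size (5446 is 73% of 7500, not about 80%);
2. the overall MACE proportion at the 288-event target;
3. the MACE proportion in women, used consistently in the 1B interaction and in 2B;
4. whether relative or absolute effects are held.

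Replace the stated 90%, 80% and 90% with the resulting figures and their range, and note that 288 is a target the DSMB may change. Do not insert single figures taken from the separate re-runs above.

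The cost is one recalculation and a few sentences in Appendix IV. Sample, conduct and primary analysis do not change. The stated powers will probably look less favourable.

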*Hypothesis C)* *Statins will decrease levels of immune activation markers to a greater extent in post-menopausal HIV-infected women versus pre-menopausal HIV-infected women.* The outcomes being tested in this sub-objective are the changes from pre-treatment to 1 year of follow-up of each of the immune activation markers tested parallel to Objective 1C. Interactions by menopause status and treatment will be tested using linear (log transformed as indicated) models, which can also incorporate covariate adjustment. Assuming a 22% female enrollment and a 5% per year loss to follow up, the effective sample size for this analysis is 1138. Assuming a 1:1 ratio of female comparison groups, the sample sizes will be 569 for the pre- and post-menopausal groups. Using analysis assumptions from Objective 1C, and under additivity assuming a 375 ng/mL effect of menopause on sCD14 differences at 1 year as well as a similar effect of statins on sCD14 differences at 1 year, there will be 80% power to detect an additive interaction of menopause and statin of 390 ng/mL.

Hypothesis D) CVD risk-reduction will be mediated in part through statin-induced immunomodulation, more so in post-menopausal (vs. pre-menopausal) HIV-infected women. Parallel to Objective 1D, the SEM model will be used to incorporate all biomarker data into a single model for CVD clinical outcome, and then to test the covariate pathways, including directionality and temporal ordering. For this sub-objective, some of these pathways to be tested include the following: direct effect of menopause status on CVD, direct effect of menopause status on immunomodulation, direct effect of immunomodulation on CVD, menopause effect on CVD through immunomodulation, direct effect of statin on CVD and on immunomodulation, and menopause effect on CVD through statin effect.

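### Appendix IV, Hypotheses 1C and 2C: the entry value of the marker is not pre-specified as a covariate in the interaction models; for sCD14, leaving it out makes the error variance 21% larger.

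*Protocol*

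**What the plan says.** Appendix IV, Objective 1, Hypothesis C defines the outcome as a change score: "The outcomes being tested in this sub-objective are the changes from pre-treatment to 1 year of follow-up of the immune activation markers tested". The sex-by-treatment interactions "will be tested using linear (log transformed as indicated) models, which can also incorporate covariate adjustment". Objective 2, Hypothesis C follows the same pattern: "Interactions by menopause status and treatment will be tested using linear (log transformed as indicated) models", with the same permission to adjust.

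Neither hypothesis lists the entry value of the marker among the model terms. The general analysis plan of Appendix IV (Overview Considerations) leaves the covariate list to be informed by comparing baseline characteristics between the groups. Its examples are race, hypertension, smoking, substance use, lipids and BMI. It gives particular weight to covariates thought to be prognostic, but does not mention the marker's own entry value.

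For sizing, Hypothesis 1C takes, for sCD14 only, "standard deviation of 1-year measurements same as baseline and intra-person correlation of 0.65". It reports that "the effective sample size for this sub-aim is 5174 persons" and that "there will be 80% power to detect an additive interaction effect of 220 ng/mL". Hypothesis 2C reuses these assumptions with 569 women per menopause group and states 80% power for 390 ng/mL.

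**The concern.** When two measurements on the same person correlate at 0.65, subtracting the entry value in full over-corrects. The entry value then adds noise that a regression coefficient on it would remove. Interaction contrasts are expensive to power, and 2C has only 569 women in each group, so avoidable noise matters more here than for a main effect.

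Leaving adjustment optional has a second cost. Two analysts following the same text could fit different models and report different interaction p-values. The main model should be fixed before the data are seen.

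**Working it through.** **Inputs.**
- Equal SDs at the two times and rho = 0.65, for sCD14 (Appendix IV, Hypothesis 1C).
- Effective N of 5174 after 5% loss (5446 × 0.95 = 5173.7). At 22% women this is about 1138 women and 4036 men.
- 569 and 569 for Hypothesis 2C.
- 1:1 allocation (main protocol, Section 9.3).
- The baseline SD of sCD14 is not printed, and neither 1C nor 2C states an alpha.

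**1. The plan's own figures.** The SD can be back-solved from Hypotheses 1A and 2A (90% power, alpha 0.0167), using SD = d / [(z_alpha + z_power) × sqrt(1/n1 + 1/n2)]. The differences of 214 (1198 vs 4248), 378 (599 vs 599) and 401 ng/mL (399 vs 799) each give about 1780 ng/mL.

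The detectable interaction is (z_alpha + z_power) × SD_outcome × sqrt(4/n1 + 4/n2). With the change-score SD, 1780 × sqrt(0.70), at 80% power:
- Two-sided alpha 0.05: 280 ng/mL (1C) and 495 ng/mL (2C).
- Two-sided alpha 0.0167: 323 and 571 ng/mL.

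The stated 220 and 390 are not reproduced. Two other settings come within 3%: baseline-adjusted variance at one-sided 0.05 (221-226 and 390-399), and a variance of SD²(1 − rho) at two-sided 0.0167 with a rank-test efficiency factor (224 and 395). Neither is documented. The steps below therefore use only ratios, which do not depend on the SD.

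**2. Error variance with and without the entry value.**
- Change score: 2(1 − rho) sigma² = 2 × 0.35 = 0.70 sigma².
- Adjusted for entry value: (1 − rho²) sigma² = 1 − 0.4225 = 0.5775 sigma².
- Ratio: 0.70 / 0.5775 = 2/(1 + rho) = 1.212, so the variance is 21% larger without the entry value. The SE ratio is sqrt(1.212) = 1.10. Adjustment cuts the variance by 17.5%.

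**3. Other markers.** The protocol gives no correlation for them. With equal SDs the inflation factor is 2/(1 + rho). As assumed illustrations, rho = 0.5 gives 1.33 and rho = 0.8 gives 1.11.

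**4. Effect on the stated power.** Suppose 80% power at 220 and 390 ng/mL rests on change-score variance.
- Detectable interactions scale by sqrt(0.825) = 0.908: 220 × 0.908 = 200 and 390 × 0.908 = 354 ng/mL.
- Power at the stated interactions is Φ[(z_alpha + 0.842)/0.908 − z_alpha]. This is 0.87 at two-sided 0.05 and 0.88 at 0.0167.

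**5. Simulation check.** 1500 trials were simulated with 1138 women, 4036 men, SD 1780, a sex shift of 214 ng/mL at entry and a true interaction of −220 ng/mL. Mean estimates were −220.8 (change score) and −218.9 (entry value added), so neither shows bias. The mean residual-variance ratio was 1.213. The ratio of the sampling variances of the two estimates was 1.17. On the log scale its simulation SE is about sqrt(4 × 0.175/1500) = 0.022, so 1.17 lies about 1.6 SE below 1.212 (ln 1.212 − ln 1.171 = 0.034).

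**6. Change or 1-year value as outcome.** The change is the 1-year value minus the entry value. With the entry value in the model, switching outcome shifts its own coefficient by exactly 1 and leaves every other coefficient and SE the same. The interaction test is identical.

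**The case against.** The plan does not rule out the entry value. Covariate adjustment is expressly allowed, and the general rule favours prognostic covariates. Hypotheses 1A and 2A expect the entry level to differ between the groups, and a correlation of 0.65 makes it prognostic for the 1-year level. An analyst following that rule could well include it. A separate ancillary analysis plan might also name it; the only SAP supplied covers the Mechanistic Substudy (A5333s). This stands as far as it goes: the gap is that adjustment is optional and unnamed. A reader who infers that the tests will be run without the entry value, or on untransformed data only, goes beyond the text.

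It is also fair that nothing invalid is proposed. Statin is randomized, so the treatment-by-group contrast on change scores is unbiased and its type I error is correct. These are two sub-hypotheses of an ancillary objective, not a primary or safety analysis.

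What the objection does not supply is a reason to leave the choice open. SAP Section 7.3 already adjusts the substudy's biomarker comparisons for baseline. It does not govern Appendix IV, but it shows that the approach is accepted within the same trial.

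**Conclusion.** The point holds as a loss of precision that costs nothing to avoid. For sCD14 the 21% follows directly from the protocol's equal SDs and correlation of 0.65, with no outside figure. It applies on the scale where those two assumptions hold. It should not be carried to other markers, for which only the formula 2/(1 + rho) is available. The gain to 87-88% power is conditional on the stated 80% resting on change-score variance. That is the natural reading of Hypothesis 1C, but its figures do not confirm it.

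A reader might infer from the failed reproduction that true power at 220 and 390 ng/mL is only about 60% (two-sided 0.05) or 42-43% (0.0167), rising to 68% or 51% with adjustment. The documents do not support stating that as fact. It needs an SD that is printed nowhere, back-solved with a two-means formula although 1A and 2A specify a rank-type test. It also needs an alpha that neither 1C nor 2C gives. The mismatch is a reason to ask for the SD and alpha behind the two figures. It does not show them to be wrong.

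The change is worth making, but it is not critical to the trial.

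**What to change.** In Appendix IV, Hypotheses 1C and 2C, state that the interaction is tested in a linear model with four terms: treatment, group (sex or menopause status), their interaction, and the entry value of the same marker on the same scale as the outcome (logged if the outcome is logged). The change score may stay as the outcome or be replaced by the 1-year value. Any further covariates can remain optional.

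The cost is a sentence in each hypothesis and in whatever analysis plan implements them. No new samples are needed. No participant is lost, because a change cannot be computed without an entry value.
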